#### 5.3 STRATEGIES FOR RECRUITMENT AND RETENTION

The aims of the proposed study target the clinical population of the PI who specializes in low vision rehabilitation with subspecialty in neurological visual impairments.

#### 5.4 PARTICIPANT WITHDRAWAL OR TERMINATION

##### 5.4.1 REASONS FOR WITHDRAWAL OR TERMINATION

Subjects have a right to withdraw from the study at any time. Additionally, the subject may be withdrawn from the study for any reasons: if it is in the best interest of the subject, intercurrent illness, adverse events, or worsening condition. The site investigators may request the withdrawal of a subject because of protocol violations, administrative reasons, or any other valid and ethical reasons.

Reasons for subject discontinuation may include, but are not limited to, the following:

- Investigator determination that it is not in the best interest of the subject to continue participation
- Serious adverse events
- Any other safety concerns

---

#### 5.4.2 HANDLING OF PARTICIPANT WITHDRAWALS OR TERMINATION

If a participant needs to withdraw early, they will be asked to accept a final telephone call at the end of the study to confirm vital status. Participants who are withdrawn due to an adverse event, serious or not, will be followed until the resolution of the event.

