#### 5.5 PREMATURE TERMINATION OR SUSPENSION OF STUDY

If the study is terminated or suspended prematurely, all enrolled participants will be notified and asked to attend a final safety visit. If there are participants with ongoing adverse events at the time of premature termination those participants will be followed until resolution of the event.

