#### 7.3.5 EARLY TERMINATION VISIT

In the event a participant is terminated from the study due to an Adverse Event, the study PI will follow the participant for at least 30 days after termination to confirm the event has resolved or the patient is receiving appropriate treatment.

---

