#### 7.3.7 SCHEDULE OF EVENTS TABLE

Procedures	VISIT 1 (ASSESSMENTS WILL BE REPEATED IF PARTICIPANT AGREES )	Visit 2 (1 week +/-2 days Visit 1 assessments will be repeated if participant agrees and the clinical staff will determine if this is clinically appropriate
Follow Up Phone Call		X
Visual Acuity (refraction if needed)	X	X
Slit Lamp Exam	X	X
NEI corneal staining scale	X	X
Baseline Video Recording	X	X
Eye Lid Prep	X	

Procedures	VISIT 1 (ASSESSMENTS WILL BE REPEATED IF PARTICIPANT AGREES)	Visit 2 (1 week +/- 2 days Visit 1 assessments will be repeated if participant agrees and the clinical staff will determine if this is clinically appropriate
Measurement of force to open the ptotic lid	X	
Polarity experiment, case 1 (apply lid magnet array)	X	
Video recording	X	X
10 point comfort and efficacy scale	X	X
spectacle magnet rotation experiment	X	
20 minute trial at optimum rotation	X	
Repeat Video Recording	X	
Repeat 10 point comfort and efficacy scale	X	
Polarity experiment, case 2 (apply lid magnet array)	X	
spectacle magnet rotation experiment	X	
20 minute trial at optimum rotation	X	
Video recording	X	
10 Point Comfort and Efficacy Scale		X
Repeat visual acuity	X	
Repeat Slit Lamp Exam	X	
Repeat NEI Nafl scale	X	
Clinical Decision		X

<Insert text>

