# 8 ASSESSMENT OF SAFETY

## 8.1 SPECIFICATION OF SAFETY PARAMETERS

The safety of the study device will be evaluated at every visit following the enrollment visit and will be defined by the incidence of related adverse events. Specifically, we will evaluate:

- **Systemic safety:** Incidence and severity of systemic adverse events during the study (adverse events spontaneously reported or observed by the Research Assistant).
- **Ocular safety:** Incidence and severity of ocular adverse events during the study (ophthalmic examination, adverse events spontaneously reported).
- **SAFETY CUTOFFS: Should visual acuity decrease more than 2 lines, worsening of corneal rating of more than 1.5 points or other ocular surface ratings more than 2 points, and comfort rating lower than 5/10; study activities will cease for at least 1 week and an adverse event report to the IRB. Serious adverse events which will result in immediate dismissal from the study (and treatment) include: 1) development of a corneal epithelial defect or infiltrate without epithelial defect or 2) broken skin on the eyelid.**

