### 8.1.1 DEFINITION OF ADVERSE EVENTS (AE)

Adverse Event (AE): Any untoward or unfavorable medical occurrence in a human subject, including any abnormal sign (for example, abnormal physical exam or laboratory finding), symptom, or disease, temporally associated with the subject's participation in the research, whether or not considered related to the subject's participation in the research.

---

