### 8.3 TIME PERIOD AND FREQUENCY FOR EVENT ASSESSMENT AND FOLLOW-UP

Adverse events or abnormal findings thought to be associated with the study device will be followed until the event (or its sequel) or the abnormal finding resolves or stabilizes at a level acceptable to the Investigator. Events that have not resolved or stabilized will be followed for 30 days post study completion. Subjects will be encouraged to follow up with their physician for the treatment of any events beyond 30 days post study completion.

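### A participant who withdraws with no recorded adverse event is offered only an end-of-study vital-status call, so eye, lid-skin or comfort problems arising after Visit 1 are captured only if volunteered

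*Combined protocol and SAP*

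**What the plan says.** All references are to the combined protocol and SAP.

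- **Early withdrawal, general rule (5.4.2):** "they will be asked to accept a final telephone call at the end of the study to confirm vital status".
- **Withdrawal for an adverse event (5.4.2, next sentence):** "Participants who are withdrawn due to an adverse event, serious or not, will be followed until the resolution of the event". Section 7.3.5 adds that "the study PI will follow the participant for at least 30 days after termination to confirm the event has resolved" or is being treated. Section 8.3 begins "Adverse events or abnormal findings thought to be associated with the study device will be followed until the event" and continues to resolution or stabilisation.
- **Early stop of the whole study (5.5):** "all enrolled participants will be notified and asked to attend a final safety visit".
- **Safety measure (8.1):** "Incidence and severity of ocular adverse events during the study", drawn from ophthalmic examination and spontaneous reports. Safety is to be evaluated at each visit after enrolment.
- **What counts as an adverse event (8.1.1):** any abnormal sign, "symptom, or disease, temporally associated with the subject's participation in the research, whether or not considered related". Section 10.4.7.1 gives mild lid discomfort as an example of a minor adverse event to be recorded when it happens.
- **Schedule (7.1.1, 7.3.7):** both arrays are tested at Visit 1, and acuity, slit lamp and corneal staining are repeated at its end, with comfort. The second column is headed "Visit 2 (1 week +/-2 days" and lists acuity, slit lamp, staining and a follow-up telephone call.
- **Reasons for leaving (5.4.1, 10.4.5):** participants may leave at any time. Possible reasons are listed, but nothing requires the reason to be asked or recorded. Withdrawals are to be summarised, with no mention of reasons.

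**The concern.** Vital status is not an outcome of this eyelid-device study. The outcomes of interest are fissure height, comfort, acuity, corneal staining and ocular or skin events. The follow-up that would capture the safety outcomes after withdrawal begins only once someone has classed the withdrawal as due to an adverse event, and no step obliges staff to ask. A participant who simply fails to return for Visit 2, or gives no reason, does not reach that route.

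Corneal staining is an examination finding, so a call about vital status cannot detect it. Spontaneous reporting is a thin safeguard in a population that includes children from age 5 and adults with MMSE scores of 18 to 23. Section 3 makes a later randomised trial depend on the endpoints being met and the device being judged feasible. Why people stopped, and how their eyes were a week later, bears on that judgement.

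**Working it through.** **1. Is there a figure to reproduce?** No. The plan states no withdrawal rate, expected event rate or safety denominator. The check is therefore a comparison of the rules, followed by an illustration on stated assumptions.

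**2. Follow-up by route of leaving**

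| Route | Follow-up specified | Eye, skin or comfort data after leaving? |
|---|---|---|
| Withdrawn for an adverse event (5.4.2 second sentence, 7.3.5) | Until resolution; at least 30 days by the PI | Yes, for that event |
| Device-associated event or finding on record (8.3) | Until resolved or stabilised | Yes, for that event |
| Whole study stopped early (5.5) | Final safety visit | Yes |
| Voluntary or unexplained, no event on record (5.4.2 first sentence) | Vital-status call | None specified |

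Only the last row is uncovered.

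**3. What that participant already has.** Someone who completes Visit 1 has acuity, slit lamp, staining and comfort recorded after exposure on that day. What is missing is the evaluation after enrolment that 8.1 calls for. In a two-visit study with baseline at Visit 1, that is Visit 2.

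**4. Timing of the call.** The Visit 2 window is 7 ± 2 days, that is, days 5 to 9 after Visit 1. The Protocol Summary gives 2 weeks for a participant and 2 to 3 years for the study. If the end of the study means the participant's own planned end, the call falls near the window. If it means the end of the trial, an early enrolee could be called 2 years or more later. The text does not say which.

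**5. Size, by illustration.** Inputs: 19 enrolled (10.5); w = number leaving with no recorded event and no later eye data, **assumed** to be 1 to 4; no events seen in the others (also assumed).

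- Number with an event: between 0/19 and w/19.
- Exact upper 97.5% limit for zero events in n participants: 1 − 0.025^(1/n). With n = 19 this is 17.6%. If the w participants were left out, n = 19 − w.

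| w | Highest possible proportion, w/19 | n if left out | Upper limit on that n |
|---|---|---|---|
| 1 | 5.3% | 18 | 18.5% |
| 2 | 10.5% | 17 | 19.5% |
| 3 | 15.8% | 16 | 20.6% |
| 4 | 21.1% | 15 | 21.8% |

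The middle column is the uncertainty that a vital-status call cannot reduce. The last column shows that the unstated choice of denominator moves the limit by 0.9 to 4.2 points (18.5 − 17.6 and 21.8 − 17.6).

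**The case against.** The strongest reply is that the plan already follows the people who matter. Anyone withdrawn for an adverse event is followed, serious or not. Discomfort meets the definition in 8.1.1, and mild lid discomfort is named as recordable. Comfort below 5/10 is among the safety cutoffs in 8.1, although the mix of *or* and *and* there leaves unclear whether it is enough alone. Section 2.3.1 tells participants with low comfort to remove the device and contact staff for a visit. The scheduled exposures are short, all at Visit 1, and followed by an eye examination the same day. The documents do not clearly say that the device is worn at home between visits. A person who does not return also counts as a non-completer against the primary endpoint, so is not invisible to the feasibility decision.

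Most of this stands, and it rules out two stronger readings that a reader might infer. One is that every withdrawn participant gets nothing but the vital-status call; the second sentence of 5.4.2, with 7.3.5 and 8.3, contradicts that. The other is that people who stop for discomfort drop out of the safety incidence. Known discomfort is an adverse event and brings follow-up, an event recorded before leaving still counts, and no text removes withdrawn participants from the denominator.

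The reply does not reach the participant who leaves with nothing recorded and is not asked why. The follow-up call listed under Visit 2 in 7.3.7 does not close the gap either: its content is not described, and 5.4.2 assigns withdrawn participants a different call.

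**Conclusion.** The point holds in a limited form. For a voluntary or unexplained withdrawal with no recorded adverse event, the plan collects no eye, lid-skin or comfort information after leaving and requires no reason. It specifies a call whose timing may miss the period of interest. This is also out of line with 5.5, which applies the principle of a final safety check to a stopped study but not to a single participant who stops.

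The size is unknown, because the documents give neither a withdrawal rate nor an event rate. Each such participant leaves 1/19 (5.3 points) of the incidence unresolved; the range to 21.1% rests on the assumption of up to 4 of them and no events in the rest. The true effect is likely to be well below that ceiling, given the examination at the end of Visit 1. How many events could arise later also depends on whether the device is worn between visits, which the documents leave unclear. This is a cheap improvement to a stated rule and does not invalidate the safety assessment.

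**What to change.** Amend 5.4.2 as follows, leaving the sentence on adverse-event withdrawals in place:

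1. Record the reason for every withdrawal, including where none is given.
2. Offer every withdrawing participant the acuity, slit lamp and NEI staining examination already scheduled for Visit 2, without further device testing.
3. If that is declined, make the telephone call in the Visit 2 window (1 week ± 2 days). Ask about comfort, vision, eye and lid-skin symptoms and any treatment sought.
4. State, there or in 10.4.4, that all participants exposed to the device stay in the safety denominator. Report withdrawals by reason, with the number lacking any assessment after Visit 1.

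The cost is protocol wording and a short call script. The examination and a telephone contact are already in the schedule, so no new procedure is needed. Some participants will decline, and the reported event rate may come out slightly higher because more events are found.

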#### 5.5 PREMATURE TERMINATION OR SUSPENSION OF STUDY

If the study is terminated or suspended prematurely, all enrolled participants will be notified and asked to attend a final safety visit. If there are participants with ongoing adverse events at the time of premature termination those participants will be followed until resolution of the event.

### 6 STUDY DEVICE

#### 6.1 STUDY DEVICE DESCRIPTION

Neodymium magnet embedded in a glasses frame and a polymer embedded (PDMS) micro-magnet array fitted externally to the upper lid with IV 3000 securement film. The IV 3000 is FDA approved for extended wear on the skin. Tegaderm, which is essentially the same adhesive, is even FDA approved as an eye covering (we used Tegaderm in early studies but switched to IV 3000 for its superior ease of handling based on packaging technique). It generates a strong bond, in a prior study keeping the magnetic array affixed to the eye lid skin for a mean of  $6 \pm 4$  days with good participant reported comfort when used for 2 hours per day during rehabilitation therapies. In order to allow doctors and patients to easily adjust the force of the MLP in the interest of maximizing their comfort and blink

quality while accommodating variability in ptosis or lid magnet positioning, we propose to further develop and test a novel approach where the force is adjusted by manually rotating the spectacle magnet with a small dial on the side of the spectacle frame. The MLP is FDA exempt as a Class 1 Device. An Investigational Device Exemption (IDE) application was not required in prior studies approved by the MEEI IRB HSC and should not be required in order to carry out this study. MLP status as a device was reviewed extensively by [name] and her team as well as by legal ([name]), last reviewed in fall 2017.

#### 6.1.1 ACQUISITION

Magnets will be acquired from SM Magnetics, Pelham AL or similar supplier. PDMS supplies will be acquired from Fisher Scientific. Frame supplies will be acquired from Designs For Vision Rokokam, NY , Michelle Moretti Eyeware and Skelmet, Boston MA.

#### 6.1.2 FORMULATION, APPEARANCE, PACKAGING, AND LABELING

Arrays will be labeled with lot and batch numbers.

#### 6.1.3 PRODUCT STORAGE AND STABILITY

Only the arrays have an expiration date. Neodymium magnets are highly stable and resistant to demagnetization. The spectacle magnets will have an expiration of 5 years. The PDMS arrays will have an expiration of 1 year. They are stored at room temperature.

#### 6.1.4 PREPARATION

Magnets are prepared by the manufacturer and coated in nickel. They will be embedded in PDMS at Schepens Eye Research Institute using a mold produced onsite with a 3-D printer.

#### 6.1.9 DURATION OF THERAPY

see other sections

#### 6.1.11 DEVICE SPECIFIC CONSIDERATIONS

The MLP is FDA exempt as a Class 1 Device and therefore an Investigational Device Exemption (IDE) application was not required in prior studies approved by the MEEI IRB HSC and should not required in order to carry out this study. MLP status as a device was reviewed extensively in the fall of 2017 by [name] and her team as well as by legal ([name]). Mass Eye and Ear has submitted a patent application for the technology, and so status was also reviewed by [name] and his team in the Intellectual Property department.

### 6.2 STUDY AGENT ACCOUNTABILITY PROCEDURES

The devices will be stored and dispensed from the lab offices at Schepens Eye Institute. Logs will be kept by the Research Assistant to keep account of which devices were used for the specific subjects. If devices are returned that will also be noted on the device logs.

## 7 STUDY PROCEDURES AND SCHEDULE

### 7.1 STUDY PROCEDURES/EVALUATIONS

#### 7.1.1 STUDY SPECIFIC PROCEDURES

A cognitive pre-screening to guide the consent process will be administered as described in section 13.3.2. After consent, participants will have their acuity measured (refraction as needed), slit lamp with Nafl & NEI scale. Next, the MLP will be placed on the patient and video recordings made for 1 minute (comfort monitored with a 10-point scale during this period). Next, the effect of force adjustment via magnet rotation on lid position will be measured. The spectacle magnet will be rotated (settings labeled 1-4, counterbalanced), and videos recorded for another minute at each rotational increment. For video recording we will have 2 cameras: 1 straight on and the other angled up (to capture upper lid apposition to globe, Fig 5d&e). Recording will be done with a blue filter and NaFl to simultaneously document tear film. Additional NaFl will be added over the trial at the clinical staff discretion as needed. Once optimal rotational increment is found, a 20 minute trial at that setting will be performed with repeat of video recording with comfort and efficacy scale. Afterwards, the array will be removed and an array with the alternative polarization will be applied. We will then record for 1 min getting comfort and efficacy data and repeating the rotation experiment followed by another 20-minute trial. At the end of the study visit we will repeat visual acuity, slit lamp with Nafl & NEI cornea scale, and video recordings with comfort scale will be repeated. As this is a fitting and optimization process, it is possible that additional visits will be necessary in order to make modifications, but these will be optional.

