**Common surgical treatments** - The most common method currently used to correct ptosis involves surgical tightening of the levator muscle, or in more severe cases, frontalis sling.[1] While these procedures are a mainstay of treatment, in our experience they have disadvantages in that they do not always restore normal blink function and over-correction may result in exposure keratitis. In severe cases of ptosis a conservative approach is needed leaving the ptosis under-corrected, and so even surgical candidates may benefit from magnetic correction.

**An effective easily adjustable and/or non-surgical treatment is needed** - Substantially less attention has been given to non-surgical approaches for ptosis, which has led to lack of effective options during the early recovery period from neurological etiologies, in cases with daily variability in the ptosis such as Myasthenia Gravis, or other cases where surgery is contraindicated. Ability for the patient to easily adjust the correction as the ptosis varies would be advantageous whether it were applied surgically or not.

**Limitations of available temporary treatments** - We believe that available temporary or non-surgical treatments are ineffective and even contraindicated for many target populations. These include taping the lid(s) open and propping the lid open with a wire on the glasses (ptosis crutch).[4] Unfortunately there is a paucity of data on safety or efficacy of the ptosis crutch or taping. The crutch has to be continually adjusted to keep the lid elevated, does not allow a complete blink,[5] and poses a risk for ocular injury during adjustment or should the patient fall. We have frequently encountered use of skin tape to elevate the eye lid, but this has potentially damaging effects on the ocular surface from incomplete eye closure.

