##### 4.2.1 PRIMARY ENDPOINTS

Completion of the 2 visit protocol with acquisition of interpalpebral fissure height during resting open without the MLP, and with the MLP over 5 adjustable force levels.

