#### 10.4.2 ANALYSIS OF THE PRIMARY EFFICACY ENDPOINT(S)

Analyses will be performed by the study staff using statistical software (STATA 14 or similar). Primary outcome is the change in interpalpebral fissure with versus without MLP, and change in interpalpebral fissure across the 5 rotation angles.

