#### 10.4.3 ANALYSIS OF THE SECONDARY ENDPOINT(S)

The effect of the five angular (rotation) angles on interpalpebral fissure during the spontaneous blink will be modeled using linear mixed-effects model, identical to that described for the primary outcome. Dependent variable will be the measured interpalpebral fissure during the 3 minima of each spontaneous blink event.

The effect of MLP compared to baseline without device will be modeled with another linear mixed effects model.

To model comfort level, we will treat the reported Likert-type data as interval data and use a linear mixed-effect model with angular position number as the fixed effect and participant and angular position number within participant-eye as random effects.

To statistically determine whether there are between-participant differences in response to angular position, we will employ profile analysis which is a multivariate statistical technique that uses multiple analyses of variance for repeated measures to test piecewise parallelism.

---

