#### 10.6.1 MASKING PROCEDURES

Only masked/blinded clinical staff will apply the lid magnets polarized either through thickness or through height (counterbalanced) to the study subjects.

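### The Visit 1 no-device recording is scheduled before all device recordings and sits outside the counterbalancing, so the with-versus-without contrast is open to within-session drift that the planned models do not adjust for

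*Combined protocol and SAP*

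**What the plan says.** Section 4.2.1 requires "acquisition of interpalpebral fissure height during resting open without the MLP" as well as with the device, and states no order. Section 10.4.2 says: "Primary outcome is the change in interpalpebral fissure with versus without MLP", and pairs this with change across the five rotation angles. The model for the first of these appears under secondary endpoints, in Section 10.4.3: "The effect of MLP compared to baseline without device will be modeled with another linear mixed effects model".

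Section 7.1.1 passes from the slit lamp to the device ("Next, the MLP will be placed on the patient and video recordings made for 1 minute") without describing a no-device recording. The rotation series follows ("settings labeled 1-4, counterbalanced"), then a 20-minute trial, then the same sequence with the other array. Section 10.6.1 says that array polarity is also counterbalanced. At the end of the visit, acuity, slit lamp and video are repeated; whether the device is on or off for that video is not stated.

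In the schedule (Section 7.3.7), the row "Baseline Video Recording" is marked for both visits. It stands above lid preparation, array application and all rows for device recordings.

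The models in Sections 10.1 and 10.4.3 use angular position with random effects for participant and for position within participant-eye. No term for time, period or order is named.

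**The concern.** Counterbalancing protects comparisons among device settings and between arrays from trends over the session. The no-device condition does not have that protection. If it is recorded once at the start of Visit 1 and the device recordings all come later, any change in resting lid position during the session is added to, or taken from, the apparent device effect.

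The documents give some reason to expect change over time. Section 2.1 motivates the device partly "in cases with daily variability in the ptosis such as Myasthenia Gravis" and describes constant frontalis effort as a burden of severe ptosis. Section 7.1.1 allows more dye to be instilled as the session goes on. Tiring of the lid would bias against the device and growing brow effort would favor it, so the direction cannot be assumed.

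What is at stake is the estimate of how far the device opens the eye. Section 3 makes a later randomized trial depend on this study's endpoints and feasibility, and this estimate would naturally inform it.

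**Working it through.** **Plan's own figure.** The documents give no expected size, variance or drift for the with-versus-without contrast, so there is nothing to reproduce on this point. The one power statement (30 subjects, 80%) concerns success across rotation forces. It reproduces (21 or more successes of 30, exact one-sided alpha 0.0214, power 0.803) but has no bearing here.

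**Length of the device phase** (durations from Section 7.1.1). Each array has a 1-minute recording, 4 or 5 one-minute settings (7.1.1 labels four; Sections 4.2.1, 10.1 and 10.4.2 say five) and a 20-minute trial:

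2 × (1 + 4 + 20) = 50 minutes, or 2 × (1 + 5 + 20) = 52 minutes.

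Lid preparation, the array change and the recordings after each trial come on top, so about 50 minutes is a minimum.

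**Assumptions for the illustration** (not in the documents): lid preparation P = 5 to 20 minutes; array change S = 5 to 10 minutes; one extra minute of recording after each 20-minute trial; a closing no-device recording 5 minutes after the last trial; linear drift. K is 4 or 5 settings. The opening no-device recording is centered at minute 0.5.

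**Mean time of the rotation recordings**
- First array: P + 1 + K/2.
- Second array: later by K + 22 + S.
- Both arrays: m = P + 1 + K/2 + (K + 22 + S)/2.
- Earliest case (P = 5, S = 5, K = 4): m = 8 + 15.5 = 23.5.
- Latest case (P = 20, S = 10, K = 5): m = 23.5 + 18.5 = 42.0.

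**Shift with the opening recording only**, per 1 mm/h of drift: (m − 0.5)/60.
- Earliest: 23.0/60 = 0.38 mm.
- Latest: 41.5/60 = 0.69 mm.
- Drift needed for a spurious 1 mm: 60/41.5 = 1.45 to 60/23.0 = 2.61 mm/h.

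**Shift with opening and closing recordings averaged.** The closing recording falls at E = P + S + 2K + 49, that is, minute 67 in the earliest case and 89 in the latest. The shift is (m − (0.5 + E)/2)/60, which simplifies to (P/2 − 12.75)/60.
- P = 5: −10.25/60 = −0.17 mm.
- P = 20: −2.75/60 = −0.05 mm.

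The remainder has the opposite sign. It arises because each 20-minute trial comes after its rotation recordings, so those recordings lie earlier than the midpoint of the two baselines.

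**What a time term alone could do.** The two arrays' rotation series lie 31 minutes (4 + 22 + 5) to 37 minutes (5 + 22 + 10) apart, and array order is counterbalanced. A slope could therefore be estimated among the device recordings. It would then have to be extrapolated back over the 7.5 minutes (8.0 − 0.5) to 23 minutes (23.5 − 0.5) between the opening baseline and the first array's mean. A closing no-device recording replaces much of that extrapolation with data.

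**The case against.** Several stronger readings are tempting, and the documents do not support them.

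- **That the no-device recording is shown always to come first.** Section 7.1.1 mentions no such recording. The order is inferred from row order in 7.3.7, and that table is not strictly chronological: its first row is a follow-up call marked for Visit 2. The Visit 1 rows do read in sequence, so the inference is reasonable. Visit 2 has a second baseline recording, but it too is listed ahead of the other video row and does not settle the matter.
- **That no closing baseline exists.** The end-of-visit video is grouped in 7.1.1 with acuity and slit lamp, so an array-off reading is plausible. In 7.3.7 the last Visit 1 video row directly follows the second 20-minute trial, with no array removal listed, which points the other way. The device status is unstated, and no analysis section says that the recording is used as a baseline.
- **That device and time are fully aliased.** The device recordings are spread over the session, so an added time term could partly separate them. None is planned.
- **That the bias is a known share of the clinically meaningful change.** The threshold of more than 1 mm in Section 10.1 is defined across rotation forces, not with versus without the device, and no drift figure is given. Variability over a day in some etiologies is not a measured drift over an hour.
- **That the whole primary outcome is affected.** The primary model in Section 10.1 concerns angular position, within device and counterbalanced.

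It is also fair to say that the film is part of the device, so its effect on the lid during wear belongs to the device effect, and that dye is already used before the device is placed. Both points shorten the list of drift sources but leave natural variation and brow effort.

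**Conclusion.** The point holds as a gap in protection. On the schedule, the Visit 1 no-device condition precedes all device recordings, it lies outside the counterbalancing, no later Visit 1 recording is identified as no-device, and no planned model adjusts for time or order. The with-versus-without contrast is thus open to within-session drift of unknown size and direction. The comparison across the counterbalanced settings is not.

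For scale only, each 1 mm/h of drift would move the contrast by about 0.4 to 0.7 mm, falling to about 0.05 to 0.17 mm when an opening and a closing baseline are averaged. These figures rest on assumed preparation and change-over times and on linearity. Averaging reduces linear drift but does not cancel it exactly. This is a cheap improvement to the design. It does not show that the contrast is in fact biased.

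**What to change.** - **Sections 7.1.1 and 7.3.7:** state for every recording whether the device is on or off, including the opening baseline, which 7.1.1 omits. Make the planned Visit 1 end-of-visit video a one-minute no-device recording taken after the second array is removed, and write that removal step in.
- **Sections 10.4.2 and 10.4.3:** include both no-device recordings in the with-versus-without model, with recording order or time as a covariate. Report the contrast against the pre-device and post-device baselines separately. Label the contrast consistently as primary or secondary.

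**Cost:** about one minute of video and one further fissure measurement per participant; less if the end-of-visit video was already meant to be array-off. **Downside:** the closing recording may carry a short after-effect of the adhesive or the device. Reporting the two baselines separately makes that visible.
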